Statistical considerations:	The primary endpoint of our study is the safety of this new robotic platform in bariatric surgery. Therefore our study is designed as a single arm, two-stage phase II study with a stopping rule for safety using the Simon's two-stage design. Considering that conventional laparoscopic bariatric procedures present a complication rate around 10%, we set the maximum acceptable threshold of complication at 25%. Type I error is assumed to be 0.05 and Type II error 0.8. Therefore a sample size of 39 patients is needed with an interim analysis at 22 patients. The stopping rule is 5 or more events at the interim analysis and robotic surgery is considered safe if less than 6 events occurred. Baseline characteristics and perioperative data will be presented as medians (IQ-range) for continuous variables or frequencies (percentages) for categorical variables. For statistical analysis SPSS Version 25 will be used. The docking time and operation time will be represented as a visual graphic with its evolution over time.
Compliance statement:	This investigation will be conducted in compliance with the CIP, the current version of the Declaration of Helsinki, ISO14155, ICH-GCP (as far as applicable) as well as all national legal and regulatory requirements.

ABBREVIATIONS

Provide a list of abbreviations used in the CIP – to be completed/adapted

AE Adverse Event

ADE	Adverse Device Effect
ASA score	American Society of Anesthesiology
ASADE	Anticipated Serious Adverse Device Effect
ASR	Annual Safety Report
BMI	Body mass index
CA	Competent Authority (e.g. Swissmedic)
CEC	Competent Ethics Committee
CIP	Clinical investigation plan
ClinO	Ordinance on Clinical Trials in Human Research (in German KlinV, in French Oclin, in Italian OSRUM)
ClinO-MD	Ordinance on Clinical Trials with Medical Devices (in German: KlinV-Mep, in French: Oclin-Dim, in Italian: OSRUM-Dmed)
CRF	Case Report Form (pCRF paper CRF; eCRF electronic CRF)
DD	Device Deficiency
DMC / DSMC	Data Monitoring Committee, Data Safety Monitoring Committee
Ho	Null hypothesis
H1	Alternative hypothesis
HRA	Federal Act on Research involving Human Beings (in German: HFG, in French: LRH, in Italian: LRUm)
IB	Investigator's Brochure
ICF	Informed Consent Form
ICH-GCP	International Council for Harmonisation – guidelines of Good Clinical Practice
IFU	Instruction For Use
ISF	Investigator Site File
ISO	International Organisation for Standardisation
ITT	Intention to treat

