11.2 Determination of Sample Size

The study is designed as single arm, two-stage phase II study with a stopping rule for safety using the Simon's two-stage design.

Literature shows a complication rate for conventional laparoscopic bariatric surgery of 10%. We expect to have similar complication rates with bariatric surgery. For calculation of the safety stopping point we set the maximum acceptable threshold of complications at 25%.

We used Simon's 2 stage design to derive the time point of an interim analysis and a stopping rule for safety, assuming Type I error to be 0.05 and Type II error 0.8.

Simon's optimal two-stage design yielded the following numbers with respect to a 25% threshold:

- Interim analysis will be done at 22 patients. If there are 5 or more events, the study will stop for safety.
- Final analysis will be done at 39 patients. Robotic surgery can be regarded as successful if less than 6 events occurred.

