11.4.4 Interim analyses

To guarantee the procedure's safety, the intraoperative and postoperative complications, as well as the postoperative mortality, will be analyzed after inclusion of 22 participant and will be presented as frequencies (percentages). The analysis will be done by the Sponsor-Investigator. If there are 5 or more events, the Sponsor-Investigator will terminate the study for safety.

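### A cheap improvement: in stage 2, end accrual at the sixth affected patient, because the only numerical safety stop acts at patient 22

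*Protocol*

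**What the plan says.** Section 11.2 introduces the design as the safety rule: "The study is designed as single arm, two-stage phase II study with a stopping rule for safety using the Simon's two-stage design". It then sets two limits. The first is "Interim analysis will be done at 22 patients. If there are 5 or more events, the study will stop for safety". The second is success if fewer than 6 events have occurred, with "Final analysis will be done at 39 patients"; the synopsis puts it as "robotic surgery is considered safe if less than 6 events occurred". Section 11.3, on statistical termination criteria, only points back to 11.2. Section 11.4.4 describes the single interim look and its consequence: "If there are 5 or more events, the Sponsor-Investigator will terminate the study for safety". Section 11.4.2 places the next safety analysis after the last participant's 30-day follow-up. Section 1.6 lists a data safety monitoring committee as not applicable.

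Other clauses bear on stopping without giving a count or a rate. Section 2.9 lets the Sponsor-Investigator terminate early if subject safety is in doubt or harm becomes evident. Sections 6.3 and 7.4 provide for stopping procedures when safety concerns arise. Section 10.4.2 requires serious adverse events to reach the Sponsor-Investigator within 24 hours.

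**The concern.** Events cannot be undone. Once six patients have had one, fewer than 6 of 39 is out of reach, and no later patient can change the verdict. The numerical rule does not react to this: it acts at patient 22 and is not read again until patient 39. The 17 patients in between are 44% of the sample (17/39). If the trial passes the interim with 4 affected patients and patients 23 and 24 are also affected, the verdict is fixed at patient 24 with 39 − 24 = 15 operations still planned.

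At stake is whether patients are operated on the new platform after the trial has failed its own safety criterion, with only an unquantified judgement to prevent it. The protocol expects the team still to be in its learning curve when the trial starts (3.5, 6.1).

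**Working it through.** **Inputs (11.2).** Reference complication rate 10%, unacceptable rate 25%, stage 1 n = 22, total n = 39, stop at 5 or more of 22, success at 5 or fewer of 39. The text has "assuming Type I error to be 0.05 and Type II error 0.8"; the second figure works only as power 0.80. Each patient counts at most once, which is the reading that reproduces the design.

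**Step 1: reproduce the plan's design.** With p the true rate,

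P(pass interim) = P(Bin(22, p) ≤ 4)

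P(success) = Σ over x = 0..4 of P(Bin(22, p) = x) × P(Bin(17, p) ≤ 5 − x)

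At p = 0.25 the five terms, x = 0 to 4, are 0.0018 × 0.7653, 0.0131 × 0.5739, 0.0458 × 0.3530, 0.1017 × 0.1637 and 0.1611 × 0.0501. They sum to 0.0498, the type I error. At p = 0.10 the same sum is 0.802, the power. An exact search over two-stage designs with these error rates returns these sizes and limits as the minimax design. (The protocol's word optimal is a separate labelling matter.)

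**Step 2: how often a sixth affected patient occurs in stage 2.** Given x affected in stage 1, stage-2 patient k carries event number 6 with probability

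C(k − 1, 5 − x) p^(6−x) (1 − p)^(k−6+x), for k from 6 − x to 17.

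Weight by P(Bin(22, p) = x) and sum over x and k. As a check, this must equal P(pass) − P(success): at 25%, 0.3235 − 0.0498 = 0.2737.

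**Step 3: operations still planned.** At stage-2 patient k, 17 − k remain. At least one remains when k ≤ 16. The expected saving per trial is the sum of probability × (17 − k). For delayed knowledge, 39 patients in a 12-month inclusion period (6.1) is 39/12 = 3.25 a month, so a complication known only at day 30 costs about 3 patients; replace 17 − k by max(0, 14 − k).

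| True rate | 10% | 15% | 20% | 25% |
|---|---|---|---|---|
| P(pass interim) | 0.938 | 0.774 | 0.543 | 0.323 |
| P(success), with or without the added stop | 0.802 | 0.451 | 0.176 | 0.0498 |
| Sixth affected patient by 39, among trials passing | 14% | 42% | 68% | 85% |
| Mean operations remaining, among trials reaching it | 5.2 | 6.1 | 7.2 | 8.3 |
| P(at least one operation avoided), all trials | 12% | 30% | 35% | 26% |
| Expected saving per trial, events known at once | 0.7 | 2.0 | 2.6 | 2.3 |
| Expected saving per trial, three-patient delay | 0.38 | 1.16 | 1.65 | 1.50 |

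**Step 4: effect on the error rates.** Success means at most 4 affected at patient 22 and at most 5 at patient 39. The added stop acts only on sequences that have already reached 6, none of which can be a success. P(success) is therefore the same at every p. Expected sample size falls from 22 + 17 × 0.3235 = 27.5 to 25.2 at 25%, and from 37.9 to 37.2 at 10%.

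**Step 5: how typical the example is.** Four of 22 followed by patients 23 and 24 both affected has probability 0.1098 × 0.10² = 0.1% at a 10% rate and 0.1611 × 0.25² = 1.0% at 25%. It is the earliest possible sixth patient in stage 2, not a usual course.

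**The case against.** A reader might infer that the design is wrong, or that the plan obliges the team to operate on to patient 39. The documents support neither. One interim and one final look is what a Simon design is, and step 1 confirms the limits. The general clauses in 2.9, 6.3 and 7.4 permit a stop at any time. The trial is open and single-centre, and under 10.4.2 a serious sixth event would reach within a day the person who can end the study. This stands in full. What remains is that none of those clauses carries a number and that no safety committee is planned.

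The means of 5.2 to 8.3 operations could also be taken as the saving. They apply only to trials that pass the interim and then reach a sixth affected patient. Per trial, the saving is at most 2.6 patients at the rates examined.

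Late patients also have value beyond the verdict. Docking and operation times are to be graphed over time (11.4.2), and late cases show whether the learning curve flattens. That loss is real, as is the upward bias of a complication rate from a trial stopped on an event. Both arise only where safety has already failed, and feasibility is secondary.

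Finally, the protocol does not say whether an event means a patient, and sets no minimum Clavien-Dindo grade. That is a separate matter: the added stop would use whatever definition the two existing limits use. If several events in one patient counted, success would be excluded no later, so the gap would be no smaller.

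**Conclusion.** The point holds as an inexpensive improvement, not as an error. The two-stage rule is the plan's only numerical safety stop, and it is silent for patients 23 to 39, although the plan's own success limit can become unreachable from patient 24 on. Closing the gap costs no power and no type I error. The gain is modest: a 12% to 35% chance of avoiding at least one operation, and an expected 0.7 to 2.6 patients per trial over true rates of 10% to 25%, or about 0.38 to 1.65 if every event becomes known three patients late.

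These figures assume independent patients with a constant rate, one count per patient, stage 1 outcomes known before patient 23, and no use of the discretionary clauses. A falling rate along the learning curve would make a sixth patient in stage 2 less likely than shown for a given stage 1 result.

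**What to change.** Add one sentence to 11.2 and repeat it in 11.3: in stage 2, accrual ends with the result not successful once the sixth patient with an event, stages 1 and 2 together, is confirmed, using the same event definition as the existing limits. Keep fewer than 6 of 39 as the condition for success, and leave the interim rule and the clauses in 2.9, 6.3 and 7.4 as they are. No new threshold is introduced; the existing limit is applied when it is reached.

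If the trial ends this way, report the number of patients and events at the stop and note that the raw complication rate is biased upward.

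The cost is the sentence, a running count of affected patients from data already collected at operation, discharge and day 30, and a shorter docking-time and operation-time series in trials that have already failed on safety.

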11.3 Statistical criteria of termination of the investigation

See 11.2

11.4 Planned Analyses

11.4.1 Datasets to be analysed, analysis populations

In the absence of contraindication (see exclusion criteria below) we will include consecutive patients which are eligible for bariatric surgery according to the SMOB-Criteria and having a robotic bariatric operation (including Sleeve gastrectomy, Y-Roux gastric bypass, Omega-loop gastric bypass) at our Adiposity Center at the Inselspital, University Hospital Bern, Switzerland.

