2.7 Patient Information and Informed Consent

The Investigators explain to each subject the nature of the investigation, its purpose, the procedures involved, the expected duration, the potential risks and benefits and any discomfort it may entail. Each subject is informed that the participation in the investigation is voluntary and that he/she may withdraw from the investigation at any time and that withdrawal of consent will not affect his/her subsequent medical assistance and treatment. The subjects are informed that he/she can ask any question, and consult with family members, friends, their treating physicians or other experts before deciding about their participation in the investigation. Enough time is given to the subjects

The subjects are informed that authorised individuals other than their treating physician may examine his/her medical records.

All subjects are given a subject information sheet and a consent form describing the investigation and providing sufficient information for the subjects to make an informed decision about their participation in the investigation. The enrolment will be performed during the outpatient consultation used to plan the bariatric procedure. The bariatric procedure will be done at least five days after this consultation, and patients can until then retract their consent if they do not want to participate in this study. No participant will be included in an emergency situation.

The formal consent of a subject, using the approved consent form, is obtained before the subject is submitted to any investigation procedure.

The subject should read, understand, and voluntarily agree before signing and dating the informed consent form, and is given a copy of the signed document. The consent form is signed and dated by the subject and the Co-Investigators (or her/his designee). The signed consent form is retained as part of the investigation records.

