6.2.3 Other methods for minimising bias

For minimization of selection bias, all consecutive patients eligible for laparoscopic bariatric surgery and meeting the inclusion criteria will be offered to participate in this study and will be prospectively included in the study.

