7. CLINICAL INVESTIGATION POPULATION

7.1 Eligibility criteria

Intervention group (robotic surgery):

Subjects fulfilling all of the following inclusion criteria are eligible for the investigation:

- Informed Consent signed by the subject
- ≥ 18 years old
- Capable of judgment
- Patient eligible for laparoscopic bariatric surgery according to the SMOB-Criteria and having a bariatric operation (including Sleeve gastrectomy, Y-Roux gastric bypass, Omega-loop gastric bypass) using Senhance™ Surgical System

The presence of any one of the following exclusion criteria will lead to the exclusion of the subject

- < 18 years of age
- Participants incapable of judgment or participants under tutelage
- Inability to follow the procedures of the study, e.g. due to language problems, psychological disorders, dementia, etc. of the participant,
- No informed consent signed
- Women who are pregnant
- High risk patients (immunosuppression, myopathy, liver cirrhosis, severe heart or lung disease, renal failure)
- Contra-indication for laparoscopic surgery
- Prior upper GI operation (such as hepatobiliary, pancreatic, gastroesophageal, anti-reflux or bariatric surgery or splenectomy except cholecystectomy) or open surgery with incision above the umbilicus

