8.2 Discontinuation or modifications of the intervention

Conversion from a robotic procedure to a laparoscopic procedure can be done for the following reason:

- Technical problem with the robotic system which does not prevent safe use of the laparoscopic technic
- Surgeon choice: at any time of the operation the surgeon can decide to perform a conversion in laparoscopy if he esteems the use of the robotic platform not appropriate or too risky

Conversion from a robotic procedure to an open procedure can be done for the following reason:

- Technical problem with the robotic system which also prevents a safe use of the laparoscopic technic
- Surgeon choice: at any time of the operation the surgeon can decide to perform a conversion in open surgery if he esteems the use of the robotic platform not appropriate or too risky
- Anesthesiological reason: if the patient does not tolerate the pneumoperitoneum

Each conversion to laparoscopic or open surgery will be reported in the secondary outcome.

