9.3.2 Operation and Hospital stay 3-4 days

Day 0:

Pregnancy test (urine)
Exclusion and Inclusion criteria will be tested
Operation

Hospital stay of 3-4 days.

After the operation and during its hospital stay, each patient will be visited at least once a day from the surgical resident. Vital signs, laboratory parameters, and clinical evaluation will help us to identify adverse events and treat them appropriately. If required, further examination such as laboratory parameters, vital sign measurements, or diagnostic (CT-Scan, Gastroscopy, Reoperation) may be requested by the surgeon.

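### Inclusion and the analysis population are tied to having the robotic operation, so an enrolled patient switched to laparoscopy before the operation starts has no place in the feasibility results

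*Protocol*

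**What the plan says.** Use of the robot is part of the inclusion criterion. Section 7.1 asks for a patient eligible for laparoscopic surgery and "having a bariatric operation (including Sleeve gastrectomy, Y-Roux gastric bypass, Omega-loop gastric bypass) using Senhance™ Surgical System"; the synopsis says the same. Section 11.4.1, the only description of an analysis population, speaks of consecutive eligible patients "having a robotic bariatric operation (including Sleeve gastrectomy, Y-Roux gastric bypass, Omega-loop gastric bypass". No all-enrolled or intention-to-treat set is defined; ITT appears only in the list of abbreviations.

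Enrolment comes before the operation. Section 2.7 states: "The enrolment will be performed during the outpatient consultation used to plan the bariatric procedure". It adds: "The bariatric procedure will be done at least five days after this consultation". Section 9.3.2 lists under day 0: "Exclusion and Inclusion criteria will be tested". The investigation schedule also marks the eligibility check at the operation visit and not at screening.

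Section 6.2.3 relies on consecutive recruitment against selection bias: "all consecutive patients eligible for laparoscopic bariatric surgery and meeting the inclusion criteria will be offered to participate in this study". Section 8.2 covers conversion from a robotic procedure and, for the surgeon's choice, says that "at any time of the operation the surgeon can decide to perform a conversion in laparoscopy". All conversions are reported as a secondary outcome. Sections 4.3 and 5.2 define feasibility by docking time, operation time, conversion rate, length of stay and rehospitalisation.

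**The concern.** Whether a patient meets a criterion that depends on the robot being used is known only after enrolment. Between the planning visit and the operation, the system may be unavailable, the trained team may be missing, or the surgeon may decide that the patient is better served by laparoscopy. The user manual quoted in section 3.2 itself says that anatomy in obese patients may call for manual instruments, and section 3.5 expects the team still to be in its learning curve. Such switches are therefore plausible.

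If these patients leave the study population, feasibility is described only in patients whose robotic operation did begin. Consecutive recruitment does not help: it acts when participation is offered, and its condition of meeting the inclusion criteria brings in the same later event. At stake is the secondary objective. A reader of the report could not tell how many planned robotic operations never started, or why.

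**Working it through.** **1. Follow each kind of patient through the text.**

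| Event after enrolment | Where the plan deals with it | Visible in the results? |
|---|---|---|
| Consent withdrawn before surgery | 8.4, 9.2.5: data kept up to withdrawal; number of premature stops reported | Yes, as a count |
| Still consenting, moved to laparoscopy before the operation starts | No rule; fails 7.1 and 11.4.1 if read literally; 8.2 addresses conversion from a robotic procedure | Not in feasibility |
| Switched after trocar access, before docking | 8.1.1 puts trocar access inside the operation; 8.2 allows conversion throughout the operation | Yes, as a conversion |
| Switched after docking | 8.2 | Yes, as a conversion |
| Device fault before the start | 10.4: device deficiencies documented from consent onwards | Recorded, but not as a feasibility outcome |

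The gap is the second row, together with the feasibility side of the last one.

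**2. Reproduce the plan's design figure, to see whether the fix touches it.** Inputs from section 11.2: 22 patients at the interim with a stop at 5 or more events, 39 in total, success at fewer than 6 events, rates 10% and 25%. With X ~ Bin(22, p) and Y ~ Bin(17, p):

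P(declared safe | p) = sum over x = 0 to 4 of P(X = x) × P(Y ≤ 5 − x).

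- p = 25%: 0.0498
- p = 10%: 0.802

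The stated 22/39 rule therefore meets a type I error of 0.05 and a power of 0.80. It needs 39 operated patients and is unaffected by how pre-start switches are reported.

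**3. Direction of the effect on feasibility.** Let n be the robotic operations started, c the conversions among them and k the pre-start switches. The literal plan shows c/n. The share of planned robotic operations not completed robotically is (c + k)/(n + k). The difference is

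(c + k)/(n + k) − c/n = k(n − c) / [n(n + k)],

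which is positive whenever k > 0 and c < n. The omission works in one direction only.

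**4. Size, with assumed counts.** Here n = 39 is the planned sample; c and k are assumptions, because the documents give neither.

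| k | c = 2: shown 2/39 = 5.1% | c = 0: shown 0/39 = 0% |
|---|---|---|
| 1 | 3/40 = 7.5% | 1/40 = 2.5% |
| 2 | 4/41 = 9.8% | 2/41 = 4.9% |
| 3 | 5/42 = 11.9% | 3/42 = 7.1% |
| 4 | 6/43 = 14.0% | 4/43 = 9.3% |
| 5 | 7/44 = 15.9% | 5/44 = 11.4% |

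Each switch adds roughly 2 to 2.5 percentage points.

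**5. A conditional check on the safety rule.** Suppose switched patients used up places among the 39, were not analysed and were not replaced, with the interim at 22 and the limit of 5 events unchanged. Replacing 17 by n − 22 in the formula of step 2, the probability of declaring a 25% rate safe is 0.059 at n = 38, 0.069 at 37, 0.080 at 36 and 0.093 at 35. Whether the documents support that premise is taken up in the objection.

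**The case against.** The strongest reply is that *having* means *planned to have*. Sections 7.2 and 9.3.1 include patients who meet the criteria at the planning visit, when nobody has yet been operated on. The day-0 check stands before the operation in the list, next to the pregnancy test. Section 11.4.1 restates whom the study will include and contains no sentence that removes an enrolled patient. This is a fair reading, and it makes the text ambiguous rather than explicit. It does not close the gap: the two readings give different denominators, and no sentence says how to count the switched patient under either.

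A reader might infer that switched patients disappear without trace. The documents do not support that. A case report form is kept for every enrolled participant (12.1.1), device deficiencies are documented from consent (10.4), premature stops are counted (9.2.5), and a switch after trocar access is a conversion. The bullet on technical problems in 8.2 has no time limit either, although it still concerns conversion from a robotic procedure.

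A reader might also infer that the safety count comes from a favourable subset and that the 22/39 rule is biased. That is not shown. Patients in whom the robotic operation was started are the natural set for that rule, and essentially the plan's own. The inflation in step 5 needs switched patients to occupy places among the 39, whereas section 6.1 describes the 39 as patients operated with the robot. Not replacing drop-outs (11.5) does not settle the matter.

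It is also right that conversion among started operations and non-completion among planned ones are different quantities, so the first is not a biased estimate of the second. For this reason the switches belong beside the conversion rate, not inside it. Lastly, analysis sets are often detailed in a statistical analysis plan, which is not shown here. The inclusion criterion and the population in 11.4.1 are nevertheless fixed by the protocol, and reasons for a switch that were not collected cannot be recovered later.

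**Conclusion.** The point holds in a limited form. Taken as written and checked on day 0, the inclusion criterion and the analysis population leave out an enrolled, consenting patient who is moved to laparoscopy before the operation starts. That makes the feasibility results more favourable as a statement about planned robotic operations. The direction follows from the algebra; the size cannot be determined. The contrast of 5.1% with 14.0% rests on an assumed 2 conversions and 4 switches and is not a forecast. If no such switch occurs, nothing changes. Enrichment with robot-suitable patients is possible but not demonstrated, and the primary safety decision is not affected on the evidence in the protocol. The correction is worth making before enrolment because it is cheap and removes a choice of denominator that could otherwise be made after the results are known.

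**What to change.** - In the synopsis, 7.1 and 11.4.1, replace *having* by *planned for* a bariatric operation using the robot.
- For feasibility, define the set as all enrolled patients planned for the robot. Report each switch to laparoscopy before the operation starts, with its reason (device, staff, surgeon's judgement including anatomy, patient choice), beside the conversion rate and not merged into it.
- State which moment separates a pre-start switch from a conversion, consistently with 8.1.1 and 8.2, so that every patient falls in exactly one category.
- State that the safety rule uses all patients in whom the robotic operation was started, including converted ones. The numbers 22 and 39 and their limits stay as they are.

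The cost is a change of wording in three places, one reason field on the case report form and one row in the feasibility table. The reported feasibility figure may become less favourable.
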